5.5.1 Annualized Bleeding Rate

For all subjects who prematurely discontinued from the study (i.e., before ObsDay 364), and who refuse to provide data on bleeds for the remaining time till ObsDay 364, the number of bleeds (and hence the ABR), will be imputed for the second 6-month period, using Multiple Imputation techniques as described below. The ABR for a subject is calculated as the number of bleeds divided by the observation period under consideration (expressed in years).

The number of bleeds during the missing observation period in PROPEL, will be imputed for subjects taking into account, additional post-PROPEL bleeding information that is provided for the subject. Post-PROPEL bleeding information obtained for a subject (either by the subject or from another BAX 855 study), will be treated as if observed within PROPEL before the imputation procedures.

For simplicity, the imputation process is described below for a single subject (since the imputation will be performed on a subject specific basis), focussing on the period of interest for the primary endpoint (2nd 6-month period). The imputation process is described in step-by-step manner.

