5.5.1.1 Primary Endpoint Imputation

The unobserved period (which is subject specific), is defined as the subject's missing observation period in PROPEL for which there is no post-PROPEL bleed information provided.

Step1: Fitting the model

- A subject specific Negative Binomial model will be fitted. The dependent variable (left-side of the model equation), is the number of bleeds in the subject's unobserved period after ObsDay 182, taken from all subjects in the same treatment arm (low level or high level), as the subject being imputed. The offset will be the logarithm of the duration (in days), of the unobserved period for the subject (LUP). Covariates (model variables) will be stratum category, race, age at baseline and total number of bleeds observed per subject (OB), calculated for all subjects in the same treatment group of the subject for imputation.

- It is desired to avoid using bleeds in the endmost observation period as part of the covariates since the number of bleeds observed in other subjects at that time might be very low or even zero. Therefore OB, is measured in the range from ObsDay 92 up to the minimum of:
 - Last ObsDay for subject being imputed.
 - ObsDay 329.
- The following example SAS[®] code can be utilized:

```
Proc Genmod Data = <Dataset>;  
  Class <Stratn> <Racen>;  
  Model <UB> = <Stratn> <Racen> <BAge> <OB> / Dist = Negbin  
    Offset = <LUP> Link = log;  
  ODS Output ParameterEstimates = <Outdata>  
Run ;
```

Where <Dataset> represents the input dataset containing all subjects in the same treatment arm as the subject being imputed, who have at least the same amount of ObsDays as the subject being imputed. <UB> represents the number of bleeds during the subject's unobserved period (up to the maximum of ObsDay 329), <Stratn> is the numeric stratum category, <Racen> the numeric race category, <BAge> the age at baseline, <OB> and <LUP> as defined above and <OutData> the output dataset containing the parameter estimates.

Step2: Predicting the Poisson Parameter and Imputing with it

- The subject-specific Poisson parameter will be predicted from the above model fitting results by using the predicted mean number of bleeds during the subject's unobserved period (Mu) as the prediction for the Poisson parameter.
- The number of bleeds for the subject to be imputed, will be for the "imputation period" (days), where the imputation period is defined as:

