Imputation Period (days) = (Date Corresponding to ObsDay 364 – Imputation Start Date)

Where imputation start date is as defined in section 5.4.2: Extended Observation Period of Efficacy.

- This “imputation period” will be treated/imputed as a Poisson random variate. The following example SAS[®] code can be utilized to obtain an estimate for the Poisson parameter:

```
Data <ImpSet>;  
  Set <Dataset>;  
  
  <Mu> = exp(1*<Intcpt> + <Beta1>*<sStrat> + <Beta2>*<sRace> +  
            <Beta3>*<sBAge> + <Beta4>*<sOB> + <LIP>);  
  Do i = 1 to 1 000  
    <ImpUB> = Ranpoi(1234,mu);  
    Iteration = i;  
    Output;  
  End;  
Run;
```

Where <Impset> represents the resultant dataset containing the 1 000 imputed bleed count values. <Dataset> is the input dataset containing the parameter estimates obtained from fitting the Negative binomial as discussed above and <Mu> our Poisson parameter as defined above. <Beta1>, <Beta2>, <Beta3> and <Beta4> the parameter estimates for <Stratn>, <Racen>, <BAge> and <OB> respectively. <sStratn>, <sRacen>, <sBAge> and <sOB> hold values specific to the subject being imputed, for numeric stratum category, numeric race category, baseline age and observed bleeds from ObsDay92 till last ObsDay for the subject, respectively. <LIP> is the logarithm of the imputation period (days) for the subject being imputed and <ImpUB> is the imputed number of bleeds during the imputation period for the subject.

Step3: Adding of Imputed Values to the Observed Values

The imputed bleed count of the subject is added to the subject’s observed bleed count (i.e. the subject’s observed bleeds after ObsDay 182), to obtain a bleed count for the complete 2nd 6-month period of the subject.

$$\text{Complete period bleeds} = \text{Observed period bleeds} + \text{Bleeds for imputation period}$$

For each subject to be imputed, the 1 000 imputed values will be merged into the full subject dataset, thus creating 1 000 replicates of imputed (complete) data sets (one for each imputation iteration).

Step4: Calculating ABR and Categorization

From this step onward we are working with all the subjects (those imputed and those not needing imputation) in the same dataset (1 000 replicates of them).

ABR is calculated as:

$$ABR = \frac{(Observed\ Number\ of\ bleeds + Imputed\ number\ of\ bleeds)}{Period\ under\ consideration\ in\ years}$$

Where period under consideration is:

- 1 year (365.2425 days) when working with the full year.

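### SAP 5.5.1.1 stops the imputation count at ObsDay 329 while the offset and prediction period run to ObsDay 364; taken literally, imputed means are too low and leavers from ObsDay 329 have no model

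*SAP*

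**What the plan says.** SAP 5.5.1 applies multiple imputation to subjects who stop before ObsDay 364 and "who refuse to provide data on bleeds for the remaining time till ObsDay 364". SAP 5.5.1.1 then sets out the steps.

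- **Outcome, Step 1 sentence:** bleeds in the subject's "unobserved period after ObsDay 182, taken from all subjects in the same treatment arm". No end day is given.
- **Outcome, code legend:** the variable UB is the count in the subject's "unobserved period (up to the maximum of ObsDay 329"). This applies to every imputed subject.
- **Offset:** "The offset will be the logarithm of the duration (in days), of the unobserved period for the subject (LUP"). The legend takes LUP as already defined. The unobserved period is the missing study time without post-study bleed data, so it ends at ObsDay 364.
- **Stated reason for 329:** "It is desired to avoid using bleeds in the endmost observation period as part of the covariates". This concerns the covariate OB, not the outcome.
- **Donors:** same-arm subjects "who have at least the same amount of ObsDays as the subject being imputed".
- **Prediction, Step 2:** "Imputation Period (days) = (Date Corresponding to ObsDay 364" minus the imputation start date). The count for this period "will be treated/imputed as a Poisson random variate".

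Protocol 14.4.1 models the bleed rate in the unobserved period. It brings in Day 329 as the end of the outcome only for subjects with more than 21 weeks in the observation period (182 + 147 = Day 329). SAP 5.8, which lists departures from the protocol's analysis, does not mention imputation.

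**The concern.** A count model with a log-exposure offset gives a correct rate only if the count and the exposure cover the same days. Here the legend shortens the count by 35 days and nothing shortens the offset. The fitted rate is then too low, and Step 2 carries it forward over a period that ends at ObsDay 364.

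This rule fills missing follow-up in the primary analysis. SAP 5.5.1.3 reuses it for spontaneous, traumatic and spontaneous joint bleeds. It is also the base that SAP 5.5.1.2 inflates by 10% to 80% in the sensitivity runs. Two competent programmers could produce different primary datasets from the same text. One reading also fails outright for late leavers, the group that the protocol's Day 329 rule was written for.

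**Working it through.** **Planning figures.** SAP 2.3 assumes 40% and 70% bleed-free with 48 per arm for 80% power. The exact power of the continuity-corrected chi-square at 48 per arm is 0.800, so the figure reproduces. It does not depend on the imputation rule; the 40% and 70% are used below.

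**Literal reading.** Let L be the last ObsDay, with L at least 182. The count covers 329 - L days and the offset covers 364 - L. At a constant rate, imputed mean / correct mean = (329 - L)/(364 - L).

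| L | Count days | Offset days | Ratio | +10% run | +20% run |
|---|---|---|---|---|---|
| 182 | 147 | 182 | 0.81 | 0.89 | 0.97 |
| 240 | 89 | 124 | 0.72 | 0.79 | 0.86 |
| 300 | 29 | 64 | 0.45 | 0.50 | 0.54 |
| 328 | 1 | 36 | 0.03 | 0.03 | 0.03 |
| 329 or later | 0 | 35 or fewer | no model | - | - |

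The +40% run restores the mean when 364 - L is at least 35 x 1.4/0.4 = 122.5 (L up to 241). The +80% run does so when 364 - L is at least 35 x 1.8/0.8 = 78.75 (L up to 285).

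**Cap on both count and offset, or on neither.** Both give a ratio of 1 at a constant rate for L below 329. In simulation with OB as covariate, capping both gave mean ratios of about 0.99 to 1.04. Its bleed-free probabilities matched the uncapped reading (low arm, Poisson draws, L = 182/240/300: 0.297/0.342/0.370 against 0.297/0.347/0.373). From L = 329 the both-capped window is empty, so late leavers still have no model.

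**Effect on the arm difference under the literal reading, 10% imputed per arm (assumed).**

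- Constant Poisson: 0.40^(147/182) = 0.477 and 0.70^(147/182) = 0.750. The change in high minus low is 0.1 x (0.050 - 0.077) = -0.3 points. Exact power at 58 per arm moves from 87.6% to 87.0%.
- Overdispersed counts (variance m + k m^2), leavers at Days 182 to 328: -0.2 to +0.2 points at k = 0.5, and -0.1 to +0.5 at k = 0.87.
- Mean ABR, 10% imputed from Day 182: low by 0.1 x (1 - 147/182) = 1.9%.

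**Why the sign varies.** Step 2 draws from a Poisson at the fitted negative binomial mean, which understates P(0 bleeds). In the low arm at k = 0.87 without covariates, (1 + 0.87m)^(-1/0.87) = 0.40 gives m = 1.40 over 182 days. Aligned windows with a Poisson draw give exp(-1.40) = 0.25. The literal reading gives exp(-1.40 x 0.81) = 0.32, and its +10% and +20% runs give 0.29 and 0.26. With OB as covariate (gamma frailty, k = 0.87, 60,000 donors and 60,000 targets per cell), P(bleed-free second period) per imputed low-arm subject, true value 0.40, is:

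| Rule | L = 182 | 240 | 300 | 328 |
|---|---|---|---|---|
| Literal reading, Poisson draw | 0.37 | 0.42 | 0.44 | 0.46 |
| Aligned, Poisson draw | 0.30 | 0.34 | 0.37 | 0.38 |
| Aligned, negative binomial draw | 0.39 | 0.37 | 0.38 | 0.39 |

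In the high arm (true 0.70) the literal reading gives 0.72/0.73/0.74/0.75, and the aligned negative binomial draw gives 0.70/0.70/0.69/0.70.

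**Smaller mismatches.**

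- The imputation start date is itself the first missing day, so subtracting it from Day 364 loses one day: 1/182 = 0.5% at L = 182 and 1/64 = 1.6% at L = 300.
- OB stops at ObsDay 329, but the value used for prediction (sOB) runs to the subject's last ObsDay.
- Donors need only match the subject's ObsDays, so a donor who leaves later adds a partial count at the full offset.
- The offset has no stated ObsDay 183 start. For L = 100 the uncapped ratio would be 182/264 = 0.69. SAP 5.5.1 says the steps focus on the second six months, so a start at 183 is probably intended.

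**The case against.** The strongest reply is that the cap belongs to the period, not only to the count. On that view count and offset both end at 329, the rate is right, and Step 2 scales it to 364. The code is offered as an example, and the protocol, which SAP 5.8 does not say has been changed, points away from the literal reading. This stands in part: the literal reading is not compelled. But LUP is used as defined before the cap appears, the legend is the only SAP text that gives UB an end day, and capping both still fails from ObsDay 329.

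The effect is also small. Subjects who supply post-study bleed data, including those who moved to the continuation study, are treated as observed, so 10% imputed may be high. The +40% and +80% runs, the worst-case run and the per-protocol comparison give further checks. That stands, and it is why the point rests on the rule and not on power.

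The low mean also partly offsets the Poisson draw, so aligning the windows alone moves early low-arm leavers from 0.37 to 0.30 against a true 0.40. That stands too and shapes the fix. The Poisson draw is specified consistently in protocol 14.4.1 and the SAP, so changing it is a separate matter of method.

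**Conclusion.** The point holds as a faulty, internally inconsistent rule in the primary analysis, and it should be fixed. Taken literally, the rule multiplies the imputed mean by 0.81 to 0.03 for leavers at ObsDays 182 to 328 and gives no model after that. The ratios assume a constant bleed rate. The arm-difference range of -0.3 to +0.5 points also assumes 10% imputed and the dispersion values shown.

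Three stronger conclusions are not supported:

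- A reader might infer that the rule inflates bleed-free proportions or favours one arm. The Poisson draw pulls the other way, and the net sign changes with dispersion and leaving day.
- A reader might infer that the +10% and +20% runs test nothing. They stay below the neutral mean under the literal reading, but for early low-arm leavers they do lower P(0) below its true value.
- A reader might take 329 as a cap on where the window starts, which would make late leavers' means too high. No wording in the SAP supports that.

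**What to change.** 1. Count UB and compute the offset over the same days, from max(last ObsDay + 1, 183) to ObsDay 364. Use each donor's own observed days in that window as exposure and leave out donors with none.
2. Restore the protocol's late-leaver condition with an estimable rule for a last ObsDay of 329 or later. One option is to fit donor bleeds over a wider window, such as ObsDay 183 to 364, with matching exposure, and scale through the log imputation period. The covariate window must not overlap the outcome; the protocol's own late-leaver outcome (to Day 329) overlaps its covariate (Day 92 to 329). Sparsity is the reason for the wider window: with 52 high-arm donors (assumed), Days 330 to 364 hold about 3.6 to 4.2 bleeds and Days 183 to 364 about 18.5 to 21.7.
3. Measure OB and sOB over the same days, and add 1 to the imputation period.
4. Draw from the fitted negative binomial and list this in SAP 5.8 as a separate change of method from protocol 14.4.1, or report it as a sensitivity analysis.

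Cost: more programming and a SAP 5.8 entry; no new data. The repair is not better in every cell. In the low arm at L = 240 the literal reading (0.42) is nearer to 0.40 than the aligned negative binomial draw (0.37), because two errors cancel. The wider late window is slightly pessimistic (at L = 340 and k = 0.87, 0.378 against 0.400 in the low arm and 0.693 against 0.700 in the high arm).

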8.5 Randomization and Blinding

This is a randomized, open-label, concurrent, dose regimen comparison clinical study. In order to minimize/avoid bias, once eligibility is confirmed, subjects will be randomly assigned to one of 2 treatment regimens with PK-guided dosing targeting FVIII trough levels of 1-3% or approximately 10% (8-12%) in a 1:1 ratio. Randomization occurs after the PK assessment and will be stratified according to subjects' pre-study treatment regimen/ABR (prophylaxis with ABR <5 vs. prophylaxis with ABR ≥5 vs. on-demand).

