5.12 Examination of Subgroups

The following subgroups will be utilized in analyses as indicated in the latest version of the Output Templates as well as the various sections to follow:

- Stratum, as derived from the pre-study ABR and pre-study treatment type, captured on the Hemophilia A Treatment History eCRF panel:
 - Pre-study prophylaxis treatment with $ABR < 5$.
 - Pre-study prophylaxis treatment with $ABR \geq 5$.
 - Pre-study on-demand treatment.

- Age groups (years) (per different regulatory standards, resulting in overlapping groups), using age at informed consent as obtained from the Demographics eCRF panel:
 - European Medicines Agency (EMA):
 - European (EU) Age Group ≥ 12 to < 18 .
 - EU Age Group ≥ 18 .
 - Food and Drug Administration (FDA):
 - United States (US) Age Group ≥ 12 to < 17 .
 - US Age Group ≥ 17 .
- Race as obtained from the Demographics eCRF panel:
 - Asian.
 - Black or African American.
 - Native Hawaiian or other Pacific Islander.
 - White.
 - Other.

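### SAP 5.5.1.1 Step 2: the example formula for imputed bleed rates multiplies one coefficient by a category code, although stratum and race are fitted as class factors

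*SAP*

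**What the plan says.** SAP 5.5.1.1, Step 1, fits a negative binomial model within the treatment arm of the subject being imputed. Stratum and race are declared by "Class <Stratn> <Racen>" and the model line is "Model <UB> = <Stratn> <Racen> <BAge> <OB> / Dist = Negbin". Stratum has three levels (Protocol 8.5: "prophylaxis with ABR <5 vs. prophylaxis with ABR ≥5 vs. on-demand"). Race has five listed categories in SAP 5.12, one of them "Native Hawaiian or other Pacific Islander".

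The Step 2 prose takes the subject's Poisson parameter to be the mean number of bleeds predicted by that fitted model. Code offered as an example follows: "<Mu> = exp(1*<Intcpt> + <Beta1>*<sStrat> + <Beta2>*<sRace>", continued with age, earlier bleeds and the log of the imputation period. The text defines "<Beta1>, <Beta2>, <Beta3> and <Beta4> the parameter estimates for <Stratn>, <Racen>, <BAge> and <OB> respectively". It says that the multipliers "hold values specific to the subject being imputed, for numeric stratum category, numeric race category", followed by age and earlier bleeds.

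The imputed counts enter 1,000 completed data sets, and SAP 7.1.2 calls the resulting comparison the primary analysis.

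**The concern.** A class factor has one estimate per level, with a reference level at zero. The fit contains no single stratum coefficient and no single race coefficient, so Beta1 and Beta2 have no defined value. Multiplying any one estimate by a code of 1, 2 or 3 treats arbitrary labels as quantities.

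The Poisson mean decides how often a non-completer is imputed as bleed-free. SAP 5.5.1.2 reuses the procedure for the 10% to 80% inflations and for the run without post-study bleed data. SAP 5.5.1.3 reuses it for the secondary endpoints. The inflations would scale up a mis-scaled mean, so they do not test for this problem.

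**Working it through.** **Inputs.** From the documents: three strata (Protocol 8.5), five races (SAP 5.12), the Step 1 and Step 2 code (SAP 5.5.1.1), 40% and 70% bleed-free, 48 evaluable per arm, about 10% dropout and 116 randomized (SAP 2.3). Fitted coefficients are not given, so every rate ratio below is an assumption.

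**Plan's own figure.** No figure is stated for the imputation. The only design figure for this endpoint, 48 per arm, reproduces: the continuity-corrected formula gives 49, and exact enumeration of the continuity-corrected chi-square at 48 per arm gives 80.05% power. This point does not change it.

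**Algebra.** Hold race, age and earlier bleeds fixed. The model's log mean for stratum s is a + b_s, with b_r = 0 for the reference level r. The printed formula gives a + B × s. For one B to serve all strata, B × s = b_s must hold for s = 1, 2, 3. At the reference level this reads B × r = 0, so B = 0 and all b_s = 0. One common B is therefore right for everyone only if the strata do not differ. The same holds for race.

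If B is instead the subject's own-level estimate, the formula gives s × b_s. That is right for the reference level and for code 1, and wrong by a factor exp((s − 1) × b_s) elsewhere.

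**Stratum illustration.** Assumptions: codes 1, 2, 3; last level as reference; stratum 1 at 40% bleed-free, so its mean is −ln 0.40 = 0.916 per 182 days. Entries are the printed-formula mean divided by the model mean, for codes 1, 2, 3.

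| Beta1 taken as | A: strata 2 and 3 at 1.5 times stratum 1 | B: strata 2 and 3 at 2.0 and 1.5 times stratum 1 |
|---|---|---|
| level 1 estimate | 1.00, 0.44, 0.30 | 1.00, 0.33, 0.30 |
| level 2 estimate | 1.50, 1.00, 1.00 | 2.00, 1.33, 2.37 |
| level 3 estimate (zero) | 1.50, 1.00, 1.00 | 1.50, 0.75, 1.00 |
| subject's own level | 1.00, 1.00, 1.00 | 1.00, 1.33, 1.00 |

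- A, level 1 estimate: b_1 = ln(1/1.5). Code 3 gets (1/1.5)^3 = 0.30 of its mean. The probability of no bleed becomes 0.40, 0.54, 0.67 instead of 0.40, 0.25, 0.25.
- B, own level: b_2 = ln(2/1.5). Code 2 has mean 1.833 × 1.333 = 2.443, so the probability of no bleed is 0.087 instead of 0.16.
- The reference level matters and Step 1 does not state it, whereas the class statement of the analysis model in SAP 7.1.2 carries a first-level reference option. With the first level as reference in A, the own-level reading gives 1.00, 1.50 and 1.5^2 = 2.25.

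**Race illustration.** Assume a log coefficient of ±0.3 for a race coded 4, with its own estimate used. The mean is off by exp(±0.3 × 3), that is 2.46-fold or 0.41-fold.

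**Effect on the endpoint.** Assume 10% per arm are imputed for the whole 182 days with rates off by a factor k. The arm proportion is 0.9p + 0.1p^k.

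- Low arm, p = 0.40: 0.44 at k = 0.25 and 0.36 at k = 4.
- High arm, p = 0.70: 0.72 at k = 0.25 and 0.65 at k = 4.
- Power at 58 per arm (normal approximation, no continuity correction, imputation variance ignored): 91% with no error; 90% if both arms are halved and 92% if both are doubled; 64% or 98% only if the arms err four-fold in opposite directions.

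**The case against.** The code is labelled an example, and the sentence before it asks for the predicted mean, which is correct. Protocol 14.4.1 likewise takes the parameter from the negative binomial model. The block is schematic: it uses placeholders, and its variable names differ slightly between code and text. A programmer reading output with one row per level would have to choose rows and could well use the right ones.

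Few subjects are exposed. Imputation applies only to those who stop early and provide no later bleed data; SAP 7.1.2.1 and 7.1.2.2 actively seek such data and treat them as observed. A subject with an observed bleed after ObsDay 182 is a non-responder whatever is imputed. The comparison on the per-protocol set (SAP 4.4 and 7.1.2), whose members did not discontinue prematurely, and the worst-case analysis (Protocol 14.4.1) do not rest on this formula.

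All of this stands, and it limits the point. It does not remove it: the variable definitions repeat the mismatch, so they cannot be read as shorthand for indicators. Even the most favourable reading, the subject's own-level estimate, mis-scales stratum code 2 and the non-reference races coded above 1, unless the estimate concerned is zero.

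A reader might infer that the imputed rates are wrong, or that the SAP mandates this rule. The documents support neither: the prose points to the correct quantity and nothing shows what was programmed. A reader might also infer a large error for reference-level subjects. If a stratum coefficient is ln 0.5, code 3 would get 0.5^3 = 0.125 of its rate, an eight-fold understatement. That requires Beta1 to be the level 1 estimate; with the own-level estimate the term is 3 × 0 = 0, which is correct.

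**Conclusion.** The point holds as an inconsistency within SAP 5.5.1.1. The printed Step 2 formula and its definitions do not, except by coincidence, produce the predicted mean that the Step 2 prose calls for. If followed literally, imputed rates for some strata and races would depend on category numbering, in the primary analysis and in the sensitivity and secondary imputations that reuse the procedure.

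Direction and size are unknown, because the documents give no coefficients, codes or reference levels for this model. The fold errors above are illustrations under assumed rate ratios and particular readings of Beta1. Because few subjects are exposed, the effect on the primary result may be small. A material change in power needed large errors in opposite directions in the two arms.

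**What to change.** In SAP 5.5.1.1 Step 2, replace the formula and the definitions of Beta1, Beta2, sStrat and sRace with one of the following:

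- the fitted model's own predicted mean for the subject, evaluated at the length of the imputation period; or
- exp(intercept + estimate for the subject's own stratum level + estimate for the subject's own race level + age term + earlier-bleeds term + log imputation period), using 0/1 indicators.

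State the reference levels in Step 1. Confirm that the program does this for the primary, sensitivity and secondary imputations, and rerun them if the literal formula was used. The cost is a few lines of text and code; the sample size is unaffected.
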